Leap Motion Blocks ® offers a platform in which the subjects can play freely with blocks- they can create blocks, grab, push, pile and throw blocks around. The subjects are guided to perform a sequence of actions in the game. First, they need to pinch and stretch with both of their hands to create several blocks. Then, they need to push, pile and throw blocks around.

B: Slum ball VR tournament ®

In Slum Ball VR Tournament®, objects such as tin cans and balls will keep flying towards the player, and the player needs to hit the upcoming objects back to specific location.

C: VR Sports- basketball ®

D: VR Sports- soccer ®

In VR Super Sports ® 10th edition- Basketball, player needs to keep grabbing a basketball and throwing it out into the basket while the participant becomes the goalkeeper of a soccer game and needs to use both of their hands to block the upcoming ball.

**Virtual reality-based rehabilitation in the treatment of sarcopenia among
residents in rural caring facilities
[Statistical Analysis Plan]**

[name]^a, [name]^b, [name]^b, [name]^a

^a Department of Rehabilitation Medicine, Cishan Hospital, Ministry of Health and Welfare, Kaohsiung, Taiwan; [name]

^b Department of Biomedical Engineering, National Cheng Kung University, Tainan, Taiwan; [name]

Project administrator: [name]., Department of Rehabilitation Medicine, Cishan Hospital, Ministry of Health and Welfare, [name]

[contact], [name]; [contact]

e-mail : [contact]

NCT number: NCT03809104

Date of the document: December, 08, 2019

[Statistical Analysis Plan]

Sample size estimation

To determine the sample size, the G*Power software (version 3.1.9.2, for Windows) was used. The alpha level and the power were set as 0.05 and 0.8. The effect size was set at high effect (0.8) and the minimal estimated sample size was 15 subjects.

Statistical Analysis

We used SPSS for Windows version 19.0 (Released 2010. Armonk, NY: IBM Corp) for all analyses. Continuous data were expressed as mean \pm SD and categorical variables were presented as absolute numbers or percentages. Normality and homoscedasticity were checked prior to each analysis. For comparisons data between participants in nursing home and daycare center, the chi-square test, independent t-test, and Mann-Whitney U test were used to test for differences in the distribution between categorized, normally distributed, and non-normally distributed variables, respectively. A change in outcome measures among baseline, 1, 2, and 3-month postVR-REH were assessed using repeated measure one-way analysis of variance (ANOVA) and a Bonferroni post-hoc test. A P value $\leq .05$ was considered statistically significant.

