Every participant went through four evaluations in this study. The first evaluation was the baseline evaluation, which was done to make sure the subjects meet the definition sarcopenia before the VR-REH. The second, third, and fourth evaluation was conducted at 4, 8, and 12 weeks after VR-REH, respectively. The primary outcomes included appendicular skeletal muscle mass (ASMM) index (ASMMI), dominant hand grip strength (HGS), and usual gait speed while the secondary outcomes were the range of motion (ROM) of joints of the dominant upper limbs, the strength of the biceps and tricepsbrachii muscles, and the scores of box and block test (BBT).

Anthropometry and Body Composition

Vector bioelectric impedance analysis (VBIA) was used in this study to measure the body composition of participants. VBIA was performed with the bioelectrical impedance vector analysis software by using the resistance–reactance graph method(6). Zeus 9.9 PLUS (Jawon Medical Co. Ltd., KungsangBukdo, South Korea) was used to analyze the body composition. The machine sent a minute electric current and measured the body composition by using personal data that have been saved (height, weight, sex, age, and newly calculated body impedance) via the tetrapolar electrode method (electrodes were located on both hands, both soles of the feet, and both ankles of participants with frequencies of 1, 5, 50, 250, 550, and 1,000 kHz and a current of 360 uA). ASMMI was defined as appendicular skeletal muscle mass (kg) divided by height squared (m^2)(7).

Measurement of dominant hand grip strength

The measurements of the HGS were determined by means of the JAMAR-Dynamometer (J A Preston Corporation, New York, USA) using all five notches. It is a hydraulic instrument measuring the isometric strength in kilograms and numerous studies have investigated the reliability of it in different older populations(8). Each participant was shown the correct handling and positioning of the instruments: they were asked to sit straight, with the upper arm in a neutral position and a 90° flexion of the elbow. The forearm was held in neutral position and the wrist at a 0 to 30° extension. The instrument was held freely: neither the hand nor the forearm was allowed to rest on a surface(9). Three measurements were done and recorded as the average of the three measurements and the participants rested for 1 minute in between measurements.

Measurement of the gait speed

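### The only analysis of change needs all four evaluations and has no missing-data rule, so any resident who missed one would be dropped from that outcome's whole comparison

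*SAP*

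**What the plan says.** The SAP, under Statistical Analysis, gives the method for change over the four time points: "A change in outcome measures among baseline, 1, 2, and 3-month postVR-REH were assessed using repeated measure one-way analysis of variance (ANOVA"), followed by a Bonferroni post-hoc test. The software is fixed for all analyses: "We used SPSS for Windows version 19.0". The only other comparison is nursing home against daycare center, so the ANOVA over time carries the efficacy conclusion.

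The protocol, under Baseline screening and outcome measurements, states "Every participant went through four evaluations in this study" and gives the timing: "The second, third, and fourth evaluation was conducted at 4, 8, and 12 weeks after VR-REH, respectively". I take these three follow-ups to be the SAP's 1, 2 and 3 months.

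The SAP, under Sample size estimation, gives "The alpha level and the power were set as 0.05 and 0.8" and then "The effect size was set at high effect (0.8) and the minimal estimated sample size was 15 subjects". It makes no allowance for attrition.

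Neither document defines an analysis set, a visit window, a rule for a missed evaluation, imputation, or a sensitivity analysis.

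**The concern.** A classical repeated-measures ANOVA needs a value at every level of the within-subject factor. The SPSS repeated-measures procedure excludes a case that lacks any level, and its Bonferroni comparisons use the same reduced set. With no other rule written down, the analysis is complete-case by default, and the SAP does not say so. A resident measured at baseline, week 4 and week 12 but absent at week 8 would contribute nothing, even to the contrast between baseline and week 12.

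Two things are at stake if visits were missed. The first is precision: measurements already taken are discarded from a very small sample. The second is bias. Participants are sarcopenic older adults in care settings, for whom illness or decline is a plausible reason to miss an evaluation. If so, the completers would be those who did better. No control arm is described, so a bias in the time effect passes straight into the study's conclusion.

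**Working it through.** **Inputs from the documents:** effect size 0.8, alpha 0.05, power 0.8, minimum N = 15, one baseline and three follow-up evaluations. **Assumed:** every missed-visit rate and all the simulation settings below.

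**1. The plan's own figure.** The documents name neither the test nor the type of effect size. A two-sided paired t-test with standardised change d = 0.8 has noncentrality d × √n on n − 1 degrees of freedom. At n = 15 this gives power 0.821, and at n = 14 it gives 0.790. The first n to reach 0.80 is therefore 15, which matches the plan and leaves no slack.

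**2. Complete cases.** Baseline is taken as always present, because it establishes eligibility. With an independent miss rate q at each follow-up, the share with all four values is (1 − q)³.

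| q | (1 − q)³ | × 15 | Rounded | Paired-test power at that n | Observed per visit, 15 × (1 − q) |
|---|---|---|---|---|---|
| 5% | 0.857 | 12.9 | 13 | 0.754 | 14.3 |
| 10% | 0.729 | 10.9 | 11 | 0.668 | 13.5 |
| 15% | 0.614 | 9.2 | 9 | 0.559 | 12.8 |

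The power column uses the paired test that reproduces N = 15. It is not the power of the planned ANOVA.

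Keeping 15 complete cases would need 15 / 0.857, 15 / 0.729 or 15 / 0.614, that is 18, 21 or 25 enrolled.

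Independence is the costlier pattern. If the losses are permanent dropouts totalling 10% or 20% by week 12, then 15 × 0.90 = 13.5 or 15 × 0.80 = 12 remain complete.

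**3. Hypothetical bias.** The settings were 400,000 simulated participants, random intercept SD 0.8, random slope SD 0.15 per visit, residual SD 0.4, and no true mean change. The SD of change from baseline to the last visit is √[(3 × 0.15)² + 2 × 0.4²] = √0.5225 = 0.72. Dropout is permanent and can occur before the third and fourth evaluations. The base rate is 10%, and the log-odds rise by 1 or 2 per unit of decline from baseline.

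| Dropout depends on | Log-odds slope | Complete | Completers' mean change | All-available-visits likelihood estimate |
|---|---|---|---|---|
| Decline seen at the previous visit | 1 | 79% | 0.055 | about 0 |
| Decline seen at the previous visit | 2 | 73% | 0.123 | about 0 |
| Decline at the missed visit itself | 1 | 78% | about 0.09 | about 0.05 |
| Decline at the missed visit itself | 2 | 72% | about 0.19 | about 0.11 |

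In SD units the first two rows are 0.055 / 0.72 = 0.08 and 0.123 / 0.72 = 0.17. The likelihood estimates were given the true covariance. In the last two rows, where data are not missing at random, somewhat over half of the completers' bias remains.

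**The case against.** The strongest reply is that the only sentence on completeness points away from a problem. Both documents are dated December 2019, after the stated January to October 2019 study period, so "Every participant went through four evaluations in this study" can be read as a report that no evaluation was missed. If that is so, nobody is dropped and the numerical effect is nil. The sentence also opens a description of the schedule and gives no count, so it may be no more than that. Either reading is open, and neither supplies a missing-data rule.

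A reader might go further and infer that the protocol defines participants as those with four evaluations, or that the reported result is already completers-only. The text supports neither. The sentence is not an analysis-set definition, and no missed visit is mentioned anywhere.

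Four further limits stand:

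- Actual enrolment is not given. Fifteen is a minimum.
- The direction of bias is plausible but not documented. The protocol requires fitness for 30 minutes of training, excludes recent infection and oxygen-dependent cardiopulmonary disease, and includes daycare attenders.
- The simulation models permanent dropout, so its figures do not describe the resident who misses only week 8.
- Deletion works outcome by outcome. One missing gait-speed value affects gait speed alone, whereas a wholly missed evaluation affects every outcome.

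It can also be said that replacing the main method is more than the gap requires. Against that, the replacement needs no new data and returns the same visit means if nothing is missing.

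**Conclusion.** The point holds as a conditional weakness in the specification. Followed as written, the SAP drops any resident who lacks one of four values for an outcome, and it does not say so. The size depends on miss rates that the documents do not give: about 13, 11 or 9 of 15 analysed at assumed independent rates of 5, 10 or 15% per visit, with fewer lost if misses cluster within people. The spurious completer gain of 0.08 to 0.17 SD of change is hypothetical and rests on dropout that follows observed decline.

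It would also be tempting to say that a mixed model cures the problem. It does so only when data are missing at random and the model is correctly specified. If misses depend on the value that was not observed, it reduces the bias without removing it. The change is worth making because it is cheap, not because harm has been shown.

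**What to change.** 1. State how many enrolled residents had all four evaluations, the number evaluated at each visit for each outcome, and the reasons for any misses.
2. Make the main analysis of change a REML linear mixed model (SPSS MIXED), with visit as a four-level fixed effect and repeated measures within participant. Include every participant with a baseline and at least one later value. Use a small-sample degrees-of-freedom adjustment and keep the Bonferroni visit contrasts.
3. Name the covariance structure in advance, with a simpler fallback if it does not converge. An unstructured matrix for four visits has 4 × 5 / 2 = 10 parameters, which is many for about 15 people. Heterogeneous compound symmetry (4 variances + 1 correlation = 5), falling back to compound symmetry (2), is one workable choice.
4. Keep the repeated-measures ANOVA as a labelled complete-case sensitivity analysis.
5. State that the model assumes data are missing at random and only reduces bias if misses depend on unobserved values.

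The SAP is dated after the stated study period, so the change should be recorded as a dated revision with both analyses shown. The cost is SAP wording and a different procedure in the same software, with no extra data. The downsides are the missing-at-random assumption and a covariance choice in a small sample. If no visit was missed, the estimated visit means are unchanged.

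### The SAP tests each primary outcome for any difference among four evaluations, with Bonferroni follow-up, but names no deciding visit or contrast and plans no confidence interval for change

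*SAP*

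**What the plan says.** The protocol, under Baseline screening and outcome measurements, lists three primary outcomes: "The primary outcomes included appendicular skeletal muscle mass (ASMM) index (ASMMI), dominant hand grip strength (HGS), and usual gait speed". It does not rank them. The same section gives four evaluations, one at baseline and three later: "The second, third, and fourth evaluation was conducted at 4, 8, and 12 weeks after VR-REH, respectively".

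The SAP's Statistical Analysis section covers change over time in one sentence: "A change in outcome measures among baseline, 1, 2, and 3-month postVR-REH were assessed using repeated measure one-way analysis of variance (ANOVA"), completed by "and a Bonferroni post-hoc test". It does not list the post-hoc pairs. The threshold is P at or below .05, which "was considered statistically significant". That threshold is not tied to a particular test, visit or outcome, and sidedness is not stated. On estimates, the only provision is that "Continuous data were expressed as mean" and SD.

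The Sample size estimation section of the SAP, like the protocol, gives: "The alpha level and the power were set as 0.05 and 0.8" and "The effect size was set at high effect (0.8) and the minimal estimated sample size was 15 subjects". The type of effect size is not given.

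**The concern.** A one-way time effect asks whether the four visit means are all equal. A rise, a fall, an early peak or a late drop can each make it significant. The Bonferroni step adds direction and locates the difference, but the plan does not say whether F or a pair is decisive, or which pair.

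The author of the report is therefore free to choose. An early rise that has vanished by the last evaluation can be presented as a significant change, and so can a real late gain, although the two mean different things for residents. If nothing is significant, no interval is planned from which to judge what size of benefit has been excluded.

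**Working it through.** **Inputs from the documents.** Alpha 0.05, power 0.8, effect size 0.8, minimum 15 subjects, four evaluations, repeated-measures ANOVA, Bonferroni post-hoc.

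**Assumptions, because the documents give no figures.** Compound symmetry with between-visit correlation ρ of 0.5 or 0.8; all six pairs tested; the mean patterns below. Shifts are in units of the SD of within-person change (dz). Under compound symmetry this SD is √(2(1−ρ)) visit SDs and is the same for every pair.

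**Step 1: the plan's own figure.** For a two-sided paired t test on one change with dz = 0.8 and n = 15, the noncentrality is 0.8 × √15 = 3.098 on 14 df. The critical t is 2.145 and the power 82.1%. At n = 14 the power is 79.0%, so the minimum is 15, as stated. Other routes tried:
- one-sided paired test: 12
- normal approximation to the paired test: 13
- two-sided two-sample t test: 26 per arm
- four-visit repeated-measures ANOVA with f = 0.8: 6, 4 and 3 for ρ = 0, 0.5 and 0.8

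Of these, only the single two-sided paired contrast gives 15 exactly.

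**Step 2: what F responds to.** F has 3 and 3 × 14 = 42 df, and its critical value is 2.83. The noncentrality is n × Σ(μ − mean μ)² / (1−ρ). If only one evaluation is shifted by dz, the sum is ¾ × dz² × 2(1−ρ), so the noncentrality is 1.5 × n × dz² and ρ cancels.
- dz = 0.8: 1.5 × 15 × 0.64 = 14.4, power 87%
- dz = 0.5: 1.5 × 15 × 0.25 = 5.625, power 45%

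The sign of the shift and the evaluation at which it occurs do not enter. A fall of 0.8 at the last evaluation alone also gives 87%.

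**Step 3: F with the Bonferroni step.** Simulation, n = 15, 50,000 trials per case. A pair counts as significant if 6 × p ≤ .05. Results for ρ = 0.5 and 0.8 agree to within about half a percentage point.

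| Result | Rise of 0.8 at second evaluation only | Rise of 0.5 at second evaluation only | Linear rise to 0.8 at last |
|---|---|---|---|
| F significant | about 87% | about 45% | about 75% |
| F and at least one pair | about 78% | about 33% | about 61% |
| F and baseline vs second | about 53% | about 16% | about 4% |
| F and baseline vs last | under 1% | under 1% | about 52% |
| Single planned baseline-to-last test | about 5% | about 5% | 82% |

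With a Greenhouse-Geisser correction, which the SAP does not mention, the two F figures for the early rise become about 84% and 40%.

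**Step 4: cost of leaving the contrast unnamed.** For the linear rise, the single contrast has 82% power at n = 15. As one of six Bonferroni pairs after F it has about 52%. Ignoring the F condition, the pair alone has about 53% and would need 23 participants for 80%.

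**Step 5: precision.** The 95% CI half-width for a mean change is t(0.975, 14)/√15 = 2.145/3.873 = 0.55 SD of change.

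**The case against.** The strongest reply is that the plan does not stop at the F test. If all pairs are run, baseline versus last evaluation is among them, it has a direction, and it is adjusted for multiplicity. With an early rise that vanishes, F plus that pair is significant in under 1% of trials, so a faithful report would rarely show a false benefit at the last evaluation. The post-hoc step also filters small transient shifts well: at 0.5 SD, 45% for F falls to about 16% for F plus baseline versus second evaluation. All of this stands.

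Three stronger readings are tempting, and the documents do not support them.
- A reader might infer that the SAP makes a significant time effect the criterion of success. It sets a significance threshold but never says that P ≤ .05 for time counts as benefit. The fault is that the criterion is absent.
- A reader might infer that a rise gone by the last evaluation must be novelty or test practice. The visits are described as weeks or months after the VR programme, which itself lasted 12 weeks. If they count from its end, such a rise could be a real effect that was later lost. F would then be detecting a true difference, and the open question is which difference the trial is about.
- A reader might infer that mean and SD will be reported by visit only. The SAP does not say so; a change score is also continuous data and could be summarised that way. What is missing is a stated estimate of change with a confidence interval.

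None of this supplies a deciding visit or pair.

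**Conclusion.** The concern holds as a gap in specification and reporting, and correcting it is worthwhile. After the full planned procedure, an early rise of 0.8 SD of change that has gone by the last evaluation still gives a significant change from baseline in about half of trials (53%), and some significant pair in about 78%. The plan does not say whether either would be the trial's result. A null finding would come without an interval.

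The sample size fits one two-sided paired contrast that is never named. That link is inferred from arithmetic, since the documents do not state the test behind the 15. For a linear rise, testing that contrast only as one of six pairs after F lowers its power from 82% to about 52%.

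The percentages rest on 15 participants, compound symmetry, correlations of 0.5 to 0.8, six pairs and the chosen mean patterns. They show how large the effect of the gap can be and do not predict this trial's result.

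**What to change.** 1. Reconcile the time origin. The protocol's evaluation times and the SAP's 1, 2 and 3 months must be stated as counted from the start or the end of the 12-week programme. Effect at the end of training and retention afterwards are different questions.
2. For each primary outcome, name one evaluation, with its time origin, and one two-sided within-person contrast from baseline. Report the mean change with its 95% CI.
3. Label the F test and the other pairs as supportive, and state that neither is evidence of benefit on its own.
4. The protocol dates the study January to October 2019 and the SAP is dated December 2019. If the data had been seen before the contrast was chosen, call it post hoc; adding it now does not restore prespecification.

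This takes a few SAP sentences, with the same data and software and no more participants. The downside is that a benefit seen only at another evaluation can no longer be claimed as the primary result. How the three primary outcomes share 0.05 is a separate issue that this change does not settle.

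### Optional gain: a step-down correction would give more power than the SAP's single-step Bonferroni post-hoc test at the same family-wise error per outcome

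*SAP*

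**What the plan says.** The Protocol (Baseline screening and outcome measurements) sets four assessments: "Every participant went through four evaluations in this study". The first is baseline, and "The second, third, and fourth evaluation was conducted at 4, 8, and 12 weeks after VR-REH, respectively". Muscle mass index, dominant hand grip strength and usual gait speed are all primary.

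The SAP (Statistical Analysis) covers these visits in one sentence, which says that changes over the four time points "were assessed using repeated measure one-way analysis of variance (ANOVA) and a Bonferroni post-hoc test". It lists no pairs, gives no divisor, and does not say whether the family is all six pairs or only the three comparisons with baseline. It mentions no step-down procedure and no correction across outcomes. The software line is "We used SPSS for Windows version 19.0".

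Under Sample size estimation, with 80% power at a level of .05, the SAP gives these inputs: "The effect size was set at high effect (0.8) and the minimal estimated sample size was 15 subjects".

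**The concern.** Single-step Bonferroni holds every comparison to the threshold that is needed when all the null hypotheses are true. Once one pair of visits has been declared different, fewer equalities can still be true, and the remaining comparisons can be tested less strictly with no breach of the family-wise level. The post-hoc tests are the only planned analysis that says at which visit an outcome changed. With about 15 participants, some real visit-to-visit changes would be reported as non-significant although an equally protected procedure would have found them.

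**Working it through.** **Inputs from the documents.** Four visits, n = 15, effect size 0.8, alpha .05, target power 0.8. The test behind the sample size and its sidedness are not stated.

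**Inputs assumed, because the documents do not give them.** All six pairs are tested. The 0.8 is the baseline-to-week-12 change divided by the SD of that change. Correlation between visits is compound symmetry 0.5, AR(1) 0.5, 0.7 or 0.8, or zero. Change is linear, saturating, an early plateau, or late only. Data are normal and nobody drops out.

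**1. Reproduce the plan's figure.** A two-sided paired t-test at .05 with standardised change 0.8 has noncentrality 0.8 × √15 = 3.10 on 14 degrees of freedom. Its power is 82.1%, and 15 is the smallest n that reaches 80%. So the stated 15 fits one comparison at unadjusted .05.

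**2. Size of the family and thresholds.** Four visits give 4 × 3 / 2 = 6 pairs.
- Bonferroni: .05/6 = .0083 for every pair.
- Holm, smallest P value first: .05/6, .05/5, .05/4, .05/3, .05/2, .05, stopping at the first failure.
- Shaffer: four means can be grouped as 4, 3+1, 2+2, 2+1+1 or 1+1+1+1, which leaves 6, 3, 2, 1 or 0 true equalities. After one rejection at most 3 can remain true, so the divisors are 6, 3, 3, 3, 2, 1.

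Every Holm or Shaffer threshold is at least .05/6, so any pair that Bonferroni rejects is also rejected by both. The first threshold is the same in all three, so the chance of at least one rejection is the same.

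**3. Power of one pair at n = 15, change 0.8 (noncentral t).**
- At .05/6: 53.1% (23 participants needed for 80%).
- At .05/3: 65.0% (20 needed for 80%).

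**4. Simulated power, baseline against week 12, six pairs, n = 15** (40,000 to 60,000 trials per scenario).

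| Procedure | Power | Gain over Bonferroni |
|---|---|---|
| Bonferroni | about 53% | – |
| Holm | 54–59% | about 1.5–6 points |
| Shaffer | 57–64% | about 4–11 points |

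The low end is the linear pattern. The high end is a plateau or late-only change with strongly correlated visits. Over all truly different pairs, Holm gains about 0.5 to 6.5 points and Shaffer about 1 to 11.5. In no simulated trial did Holm lose a Bonferroni rejection.

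**5. Sensitivity to the assumptions.** If the week-12 change is 0.5, Holm gains 0.3 to 1.5 points. With changes of 1.2 to 2.4, its gain on adjacent visits reaches 12 to 25 points. If the family is only the three baseline comparisons, Holm (.05/3, .05/2, .05) gains 0.1 to 14.7 points at week 12 over Bonferroni at .05/3.

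**6. Family-wise error within one outcome.** In the plateau and late-only patterns three equalities are true, so Bonferroni spends at most 3 × .05/6 = 2.5%. Simulated values were 2.2–2.4% for Bonferroni, 3.3–4.2% for Holm and 4.3–4.4% for Shaffer. With no change at any visit all three gave 4.1–4.3%.

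**The case against.** **Bonferroni is standard and valid.** This stands. A reader might infer that the plan contains an error, or that .05/6 is wrong. The documents do not support that: nothing is contradictory or anti-conservative, and the point concerns efficiency alone.

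**Six pairs is an inference.** This stands. Six is the natural reading of an unqualified post-hoc test over four visits, but three comparisons with baseline would also fit the text. The gain from Holm survives under either reading; Shaffer's divisors do not.

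**The extra rejections use real error slack.** This stands in part. Each outcome stays within .05, but the SAP corrects nothing across the three primary outcomes. If those were independent (an assumption), 2.4% each becomes 1 − 0.976³ = 7.0%, and 4.4% each becomes 1 − 0.956³ = 12.6%. This has to be disclosed. It does not remove the gain, because Bonferroni across visits was never a control across outcomes.

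**Timing.** The Protocol places the study in January to October 2019, and both documents are dated 8 December 2019. A looser correction adopted after that could look data-driven. The documents do not show whether results had been seen, so the answer is labelling and side-by-side reporting.

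**A larger loss lies elsewhere.** True: going from 82% to 53% dwarfs what Holm returns. Naming the three baseline comparisons in advance recovers about 12 points (53% to 65%) even with plain Bonferroni. That complements a step-down rule and does not argue against one.

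**Conclusion.** The point holds as a cheap improvement. The ordering of the procedures is a mathematical fact and needs no assumption. The size does: with six pairs, n = 15 and a week-12 change of 0.8, Holm adds about 1.5 to 6 points to a power of about 53% for baseline against week 12, and Shaffer about 4 to 11. A reader might take such a range as a fixed amount that the plan gives away. The documents do not support that, since they state no SD, no between-visit correlation and no time course, and the upper end needs both Shaffer's procedure and a favourable pattern. A reader might also infer that the trial becomes more likely to find some change; it does not, because the first rejection faces the same threshold in every procedure.

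**What to change.** In the SAP's Statistical Analysis sentence, name the family and replace the Bonferroni post-hoc test with Holm's step-down. Suggested content:

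- *For each outcome, unadjusted two-sided paired P values for [all six pairs of visits / the three comparisons with baseline] are ordered from smallest to largest and tested by Holm's procedure at family-wise .05, stopping at the first non-significant result.*
- *Thresholds: .05/6, .05/5, .05/4, .05/3, .05/2, .05 for six pairs; .05/3, .05/2, .05 for three.*
- Shaffer's divisors 6, 3, 3, 3, 2, 1 may be used instead, but only if all six pairs are the family.

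Cost: one sentence, and ordering the unadjusted P values by hand. Three downsides should be stated. Step-down tests have no simple matching simultaneous confidence intervals, so show Bonferroni intervals beside them. Actual family-wise error moves closer to .05 within each outcome, while the three primary outcomes remain uncorrected against each other. And the change should be dated and labelled as made after the stated study period, with the Bonferroni results also reported.
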